## **Statistical Analysis Plan**

FORCE: Focus on Reducing Dose-Limiting Toxicities in Colon Cancer with Resistance Exercise

The intervention will begin within the first weeks of adjuvant chemotherapy and will continue until 2 weeks past the last chemotherapy cycle (i.e., “end-of-study”). The intervention will include twice-weekly training sessions.

## **DESCRIPTION OF PRIMARY ENDPOINTS**

### **1.1 Chemotherapy completion rates**

Relative dose intensity (RDI) will be calculated for each chemotherapy agent as well as average relative dose intensity (ARDI), which considers all chemotherapy agents in a regimen. We will examine differences in overall RDI for each chemotherapy agent and the ARDI across regimens between the RT group and the UC group.

RDI will be calculated as Delivered dose intensity (DDI) / Standard dose intensity (SDI). SDI will be calculated as the starting dose/m^2 multiplied by number of planned cycles by total number of days from day 1 of first cycle after randomization to last planned dose of that drug. DDI will be calculated as the sum total of dose/m^2 for each of the cycles that occur between randomization and follow-up, divided by total number of days from day 1 of first cycle after randomization to last actual dose of that drug. Calculation of DDI will include missed cycles similar to Weycker's method. Thus, our measure of RDI incorporates dose reduction/modification, treatment delay, and early stoppage.

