3.6.1 From Section D. Study overview of the original KPNC application approved 2017

3. How many participants will be enrolled in this study, or how many electronic records or medical records will be used? Provide your best estimate if you are not sure

Number of KPNC participants or records:	Approximately 115 participants to be enrolled
Records used:	Approximately 7500 KPNC records used
Number of non-KPNC participants or records:	Approximately 65 participants enrolled
Total number of participants or records:	Approximately 180* participants enrolled

**Due to the impact of the COVID-19 pandemic on the study, we estimate that the total number of participants will be within the range of 10% above the original total of 180 participants.*

3.7 Enrollment and baseline testing:

Eligible participants who agree to participate will be scheduled for their first intervention visit at the earliest possible chemotherapy visit but by the third infusion visit. See Table 3 for details regarding the enrollment window based on the specific chemotherapy regimen

Table 3. Chemotherapy Regimens and Timeline

WEEK

Regimen name & drugs	Cycle	# cycles	1	2	3	4	5	6	7	8	9	10	11	12	13	14	15	16	17	18	19	20	21	22	23	24	25	26	27	28	29	30	31	32												
mFOLFOX 6 - 3 months Oxaliplatin, Leucovorin, 5FU	14 days	6 cycles	IV		IV		IV		IV		IV		IV																																	
			Day 1												8 Weeks																															
mFOLFOX 6 - 6 months Oxaliplatin, Leucovorin, 5FU	14 days	12 cycles	IV		IV		IV		IV		IV		IV		IV		IV		IV		IV		IV		IV		IV																			
			Day 1																				20 Weeks																							
Capecitabine only oral Capecitabine 2x daily for 14 days, then 1 week off	21 days	8 cycles	Oral		Oral		Oral		Oral		Oral		Oral		Oral		Oral		Oral		Oral		Oral																							
			Day 1																		18 Weeks																									
CAPEOX - 3 months Oxaliplatin infusion, day 1; oral Capecitabine 2x daily for 14 days, then 1 week off	21 days	4 cycles	IV		IV		IV		IV																																					
			Day 1												8 Weeks																															
CAPEOX - 6 months Oxaliplatin infusion, day 1; oral Capecitabine 2x daily for 14 days, then 1 week off	21 days	8 cycles	IV		IV		IV		IV		IV		IV		IV		IV		IV		IV		IV		IV		IV																			
			Day 1																		18 Weeks																									
5FU/Leucovorin Leucovorin and 5FU repeated weekly X 4-6, rest 2 weeks, start again	8 days	4 cycles	IV							IV							IV							IV																						

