			Day 1																												28 Weeks															
sLV5FU2 Leucovorin, followed by 2 day continuous infusion 5FU, repeated every 2 weeks	2 days	12 cycles	IV		IV		IV		IV		IV		IV		IV		IV		IV		IV		IV		IV		IV																			
			Day 1																				20 Weeks																							

INTERVENTION
DRUG
VISIT

A research assistant will either conduct eConsent over the phone or by video conference or meet the participant in person to complete the consent forms. The baseline visit will most likely occur as an add-on to the first or second chemotherapy infusion session or another clinical appointment, so as to avoid the need for additional visits to the clinic or cancer center for the study. If scheduling of the baseline or follow-up visits at the clinic is not convenient for the participant, the research assistant will also be available to conduct these study visits at the participant's home.

After the participant consents to be in the study (see Appendix 13.3), we will complete questionnaires with the participant as part of the baseline visit (e.g. physical activity assessment and physical function testing, see Appendix 13.5, FFQ, see Appendix 13.6.1, SF-36, and demographics, see Appendix 13.4), as well as a patient-completed side effects questionnaire

(see Appendix 13.7.3). In addition, body composition will be assessed using anthropometrics collected at the baseline visit, a DXA (see Appendix 13.8) to be scheduled as soon as possible, prior to initial intervention, and creatine dilution (see Appendix 13.8.3). Also, at the baseline visit, we will arrange for research blood draw, when possible to be coordinated with clinical blood draw that the patient receives as part of clinical care (either that visit or next chemotherapy visit but prior to starting intervention).

3.8 Interventions for experimental group:

Table 4. Intervention Terminology

Chemotherapy Cycle	A cycle of chemotherapy from infusion visit to the next infusion visit, usually this will be 2-3 weeks
Chemotherapy Infusion Visit	Date on which the participant receives chemotherapy infusion at the cancer/medical center.

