At the initiation of adjuvant chemotherapy, we will ascertain planned treatment course for participants, including planned cumulative dose and planned treatment duration. We will then examine the EMR for changes in chemotherapy dose and timing. The following variables will be defined for each drug administered:

- Planned dose intensity (mg/week) = planned total dose / planned duration of therapy (weeks)
- Actual dose intensity (mg/week) = actual total dose (mg) / actual duration of therapy (weeks)
- Relative dose intensity (RDI) (%) = actual total dose intensity / planned total dose intensity
- Average relative dose intensity (ARDI) (%) = the average across all regimens of the relative dose intensity
- Number of cycles of chemotherapy and date of initiation of each cycle

In addition, we will report on early stoppage by calculating actual number of cycles / planned number of cycles of adjuvant therapy. We will only consider dose reductions that occur after start of intervention. Chemotherapy treatment forms will be used to capture data from the EMR on chemotherapy administration (see Appendix 13.7.4). A researcher will record all relevant chemotherapy treatment variables in an online REDCap form.

4.12 Chemotoxicity:

Total combined number of moderate and severe chemotherapy-associated toxicities, assessed via medical record review, patient-completed NCI PRO-CTCAE and patient-completed side effects questionnaires. As shown in the Appendix, we will use a series of validated questionnaires for chemotherapy-associated side effects including NCI PRO-CTCAE and a questionnaire on neurotoxicity utilized in a recent phase III trial with oxaliplatin⁴⁸. See Appendix 13.7. Throughout the intervention, the research manager or assistant will email a secure web-link to the patient requesting completion of the NCI PRO-CTCAE questionnaire in advance of his/her next chemotherapy infusion visit. A researcher will record all relevant chemotoxicity variables in an online REDCap form. Participants will complete the patient-completed side effects questionnaire and NCI PRO-CTCAE questionnaire in online REDCap surveys.

4.13 Inflammatory blood measures:

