9. STATISTICAL CONSIDERATIONS

9.1 Study design:

This randomized controlled trial of resistance training intervention in colon cancer patients receiving chemotherapy consists of two arms: an in-person and telephone-based intervention to promote home-based resistance training, and a wait-list, control group. After consent and baseline visit measurements, randomization assignment will utilize a covariate adaptive randomization procedure which ensures that equal numbers of patients are assigned to each study arm and that the two arms remain balanced on five key characteristics: site of participation [Kaiser Permanente vs Penn State vs Dana-Farber]; gender [male vs female]; cancer stage [stage II vs stage III], and duration of chemotherapy [3 months vs 6 months]; planned chemotherapy regimen [FOLFOX vs CAPOX vs capecitabine vs 5-FU/LV]. This randomization method (also known as the minimization method) has been demonstrated to outperform simple randomization or stratified randomization in terms of achieving balanced groups, particularly in smaller trials with multiple important prognostic factors.

The primary objective of this trial is to compare the effect of a RT intervention versus a wait-list control on chemotherapy dose reductions, dose delays, early discontinuation of chemotherapy and treatment-related toxicity. The secondary objective is to compare the effect of the intervention versus wait-list control on changes in inflammatory biomarkers, and the tertiary objective is to compare pre and post intervention pharmacokinetics of 5-FU and oxaliplatin. The d3 Creatine objective is to compare the effect of a RT intervention versus a wait-list control on d3 creatine muscle mass at 6 months.

9.2 Sample size, accrual time and study duration:

One hundred and eighty (180) participants will be recruited and randomized over a total of 3.5 years. Patient involvement and data collection will last approximately 6 months.

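### SAP 1.1 does not limit the planned cycles in the reference dose intensity to those after randomization, so, read as written, a fully treated patient can score an RDI well below 100%

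*SAP*

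**What the plan says.** SAP 1.1 defines RDI as delivered dose intensity (DDI) over standard dose intensity (SDI).

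- SDI: the starting dose per m² is "multiplied by number of planned cycles by total number of days from day 1 of first cycle after randomization to last planned dose" of the drug. The day count starts at the first cycle after randomization. The cycle count has no stated start, and no division is stated.
- DDI: dose per m² is summed "for each of the cycles that occur between randomization and follow-up", then "divided by total number of days from day 1 of first cycle after randomization to last actual dose of that drug". Here both the cycles and the days start after randomization, and the division is explicit.

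Three protocol passages fix how many cycles can precede randomization. Section 3.7 schedules the "first intervention visit at the earliest possible chemotherapy visit but by the third infusion visit". The same section adds: "The baseline visit will most likely occur as an add-on to the first or second chemotherapy infusion session". Section 9.1 gives the order: "After consent and baseline visit measurements, randomization assignment will utilize a covariate adaptive randomization procedure".

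Protocol 4.11 defines planned dose intensity differently, as planned total dose over planned total duration. In its early-stoppage ratio, planned cycles means the whole adjuvant course. SAP 2.2 analyses RDI by linear regression and, at the 85% and 70% cut points, by logistic regression.

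**The concern.** The two halves of the ratio need not cover the same cycles. A cycle given before randomization can be counted as planned in SDI, but it can never be counted as delivered in DDI. RDI would then partly measure how far into chemotherapy a patient was when randomized. That number is neither a minimization factor (Protocol 9.1) nor a pre-specified covariate (SAP 2.2).

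RDI is one of the two primary endpoint families, alongside patient-reported toxicity. At stake are the reported RDI levels, the classification at the two cut points, and some precision. Two analysts working from SAP 1.1 could also compute materially different values for the same patient.

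A smaller gap sits in the same sentence: the SAP does not say which cycle's dose is the starting dose.

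**Working it through.** **The plan's own figure.** Protocol 9.3.4 gives a detectable difference of 0.42 SD with power 0.80 and two-sided alpha 0.05. With 90 per arm (SAP 2.1), the normal approximation gives (1.960 + 0.842) × √(2/90) = 0.418 SD, and the exact t calculation gives 0.420. With the stated SD of 17.3, 0.42 × 17.3 = 7.27, so the stated 7.3 points reproduces.

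**Units.** Read literally, SDI is dose × cycles × days and DDI is dose / days. Their ratio is not a percentage. The rest takes the SDI wording as division, to match DDI.

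**RDI for full dose, on time.** Let D be the dose per cycle, N the planned cycles (Protocol Table 3), k the cycles before randomization (0, 1 or 2), and T the days from the first post-randomization cycle to the last dose. T is the same in both halves because nothing is delayed.

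- DDI = D(N-k)/T
- SDI, with planned cycles unrestricted = DN/T
- RDI = (N-k)/N

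Example: 3-month mFOLFOX6 with N=6 and k=2. T = (6-2-1) × 14 = 42 days, DDI = 4D/42, SDI = 6D/42, RDI = 66.7%.

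| N (regimens) | k=1 | k=2 |
|---|---|---|
| 12 (6-month mFOLFOX6, sLV5FU2) | 91.7% | 83.3% |
| 8 (capecitabine, 6-month CAPOX) | 87.5% | 75.0% |
| 6 (3-month mFOLFOX6) | 83.3% | 66.7% |
| 4 (3-month CAPOX) | 75.0% | 50.0% |

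At k=1 the 4- and 6-cycle regimens fall below 85%. At k=2 every regimen does, and the 4- and 6-cycle regimens also fall below 70%. If SDI counts only the N-k remaining planned cycles, every entry becomes 100%.

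**Effect on power (illustration).** The documents give neither the regimen mix nor the distribution of k. Assumed: true RDI mean 90 and SD 17.3; mix A is 60/20/0/20% and mix B is 30/30/10/30% for FOLFOX-12, FOLFOX-6, CAPOX-8 and CAPOX-4. Let s = (N-k)/N. Regimen and duration are covariates, so only the within-regimen spread of s adds residual variance:

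- residual variance = 17.3² × E[s²] + 90² × (mean within-regimen variance of s)
- detectable true difference = 0.42 × residual SD / E[s]
- share below 85% = average of Φ((85/s - 90)/17.3)

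Worked case, mix A with k equally often 0, 1 and 2: E[s] = 0.867, E[s²] = 0.770, within-regimen variance = 0.0148. The SD is √(230.6 + 120.0) = 18.7, and 0.42 × 18.7 / 0.867 = 9.1 points.

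| k = 0/1/2 (%) | Detectable difference, A / B | Share below 85%, A / B |
|---|---|---|
| 100/0/0 | 7.3 / 7.3 | 39% / 39% |
| 0/100/0 | 7.3 / 7.3 | 67% / 73.5% |
| 80/20/0 | 7.6 / 7.8 | 44% / 46% |
| 10/80/10 | 7.9 / 8.1 | 66% / 72% |
| 50/40/10 | 8.4 / 8.8 | 55% / 58% |
| 20/60/20 | 8.4 / 8.9 | 65% / 70% |
| equal thirds | 9.1 / 9.8 | 64% / 68% |

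**The case against.** The best reply is that the SAP never says all planned cycles. The SDI sentence names a window that opens at the first cycle after randomization, and planned cycles can be read as those inside it; RDI is then 100%. Protocol 4.11 points the same way: "We will only consider dose reductions that occur after start of intervention". It is also uneven to repair the missing division and leave the cycle count unrepaired. This stands as far as intent goes: the authors may well have meant the matched version. It does not rescue the text. The neighbouring DDI sentence states the restriction and the SDI sentence omits it, and Protocol 4.11 uses planned cycles for the whole course. The reference to a published method for missed cycles does not help, because a patient treated on time has none.

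A reader might infer a bias between arms. The documents do not support that: k is fixed before randomization and is balanced in expectation, so the test remains valid under the null.

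A reader might also point out that a true 7.3-point difference becomes 7.3 × 10/12 = 6.1 (N=12, k=2) or 7.3 × 2/4 = 3.7 (N=4, k=2) and call that lost power. At a fixed regimen and k, the SD shrinks by the same factor, so the standardized effect is unchanged. Only spread in k costs power, and the upper values in the table rest on an assumed even spread. The protocol expects baseline mostly at the first or second infusion, which argues for less spread. The normal model is also crude: it puts about 28% of patients above 100%, and the mixes omit capecitabine alone and 5-FU/LV.

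Finally, Protocol 4.11's start-of-intervention anchor has no counterpart in controls. Amending it would add little, because the SAP already anchors on randomization in both arms.

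**Conclusion.** The definition is defective as written and needs correcting. With division assumed, it gives a fully treated patient an RDI of (N-k)/N: 83.3% to 91.7% for 12 cycles, and down to 50% in the extreme case of 3-month CAPOX with two cycles before randomization. These values need only Table 3, the enrollment window and the SAP formula.

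The consequences are lower RDI in both arms, fully treated patients classed below 85% or 70%, and added noise to the extent that k varies. The cut-point results suffer even when power for the mean does not: with k=1 for everyone, the detectable difference stays at 7.3 points while the illustrated share below 85% rises from 39% to 67% or more. If k varies, the detectable true difference is about 7.6 to 9.8 points over the distributions tried. That range is illustrative and should not be quoted as the trial's actual loss.

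The documents do not show that the authors intended the unmatched version or that the analysis code uses it.

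**What to change.** In SAP 1.1, state that SDI is the starting dose per m² times the number of planned cycles counted from the first cycle after randomization, divided by the planned days over those same cycles. State that DDI uses the same set of cycles. Then check that the analysis code does this, and rerun RDI, ARDI and the cut-point models if it does not.

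State also which cycle's dose is the starting dose. Using the first cycle of the course charges an earlier reduction to the trial period. Using the first cycle after randomization leaves such reductions out of RDI. This decides what RDI measures, and the choice is the sponsor's.

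The cost is a small change of wording and a code check. Protocol 4.11 already has planned dose and duration, delivered dose and cycle dates collected, so no new data are needed.

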2. OBJECTIVE

2.1 Primary Objective:

To examine differences in dose reductions, dose delays and early stoppage for chemotherapy and the total combined number of moderate and severe chemotherapy-associated toxicities between intervention group and waitlist controls.

2.2 Secondary Objectives:

2.2.1 Examine specific inflammatory markers (CRP, IL-6, TNF- α receptor II [TNF-RII]) in relation to baseline MM and FM and examine differences in changes in inflammatory markers between intervention group and waitlist controls.

2.2.2 Examine the impact of intervention versus control and RT-induced body composition changes on the pharmacokinetics [PK] of 5-FU and oxaliplatin between baseline and 4 months of RT.

2.3 d3 Creatine Objectives:

2.3.1 Test whether resistance training during chemotherapy (FORCE intervention group v. control) increases d3 creatine muscle mass at 6 months.

2.3.2 Evaluate the association of d3 creatine muscle mass with changes in functional status and strength during chemotherapy.

2.3.3 Evaluate the association of d3 creatine muscle mass with chemotherapy toxicity and relative dose intensity.

2.3.4 Evaluate the association of d3 creatine muscle mass with cancer-related biomarkers, including inflammation, CEA levels and cardiometabolic risk factors.

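### The delivered-dose denominator in SAP 1.1, read alone, does not penalise stopping a drug early, and the missed-cycle adjustment that might do so is not defined

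*SAP*

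**What the plan says.** The primary objective in Protocol 2.1 begins "To examine differences in dose reductions, dose delays and early stoppage for chemotherapy". SAP 1.1 makes RDI, per drug and averaged over the regimen, the measure of this.

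The SAP divides delivered dose intensity (DDI) by standard dose intensity (SDI). SDI is the starting dose "multiplied by number of planned cycles by total number of days" from the first post-randomization cycle to the last planned dose. DDI sums the dose "for each of the cycles that occur between randomization and follow-up", and that sum is "divided by total number of days from day 1 of first cycle after randomization to last actual dose of that drug".

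Two further sentences follow. One says "Calculation of DDI will include missed cycles similar to" a named method. The other concludes: "Thus, our measure of RDI incorporates dose reduction/modification, treatment delay, and early stoppage".

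Protocol 4.11 divides actual total dose by actual duration of therapy, has no missed-cycle rule, and handles stopping through a separate measure: "In addition, we will report on early stoppage by calculating actual number of cycles / planned number of cycles of adjuvant therapy". SAP 2.2 analyses RDI by linear regression and by logistic regression at the 85% and 70% cut points. In the text available for review it lists no analysis of the cycles ratio.

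**The concern.** The two time bases end at different events. For a patient who finishes late, this is what makes delay count. For a patient who stops for good, the delivered time base ends with the last dose, so the lost cycles leave both the dose sum and the time. The stated formula then lacks a property that the SAP claims for it.

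The missed-cycle sentence could repair this, but only if it keeps the days of cycles after the stop in the denominator. Entering those cycles as zero dose in the sum changes nothing. The dose sum is also limited to cycles up to follow-up. Protocol Table 7 places that visit within two weeks of the last chemotherapy cycle. If that means the last cycle given, most ungiven cycles fall outside the window.

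Two competent programmers could therefore give the same patient about 110% or 50% on a primary endpoint.

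**Working it through.** **Inputs.** Protocol Table 3: six-month mFOLFOX6 is 12 cycles of 14 days; CAPOX is 8 or 4 cycles of 21 days. Protocol 4.14: the 5-FU infusion ends at about 46 hours. SAP 2.2: cut points 85% and 70%. Protocol 9.3.4: SD 17.3, detectable difference 0.42 SD.

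**Assumptions.** SDI is read as a quotient, because as a product DDI/SDI would not compare like with like. Planned cycles are counted after randomization. Doses are full and on time unless stated. All stop rates are assumed.

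**The plan's own figure.** A two-sided t-test with 90 per arm, 80% power and alpha 0.05 detects 0.420 SD; 0.42 × 17.3 = 7.27, so the stated 7.3 points is reproduced. The plan gives no worked RDI value.

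**Literal formula.** Let N be planned cycles, k cycles given, c cycle length in days, q mean dose fraction, d days of delay, and t days from cycle day 1 to that cycle's last dose:

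RDI = [kq / ((k−1)c + t + d)] / [N / ((N−1)c + t)]

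FOLFOX, N = 12, stopped after 6:

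- Day-1 drug, t = 0: (6/70)/(12/154) = 110.0%
- Same, days counted inclusively: (6/71)/(12/155) = 109.2%
- Two-day infusion, t = 2: (6/72)/(12/156) = 108.3%
- Time run to cycle end: (6/84)/(12/168) = 100.0%
- Untreated planned time kept: (6/154)/(12/154) = 50.0%

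Two patients on the same plan share one SDI, so it cancels. That the stopper scores no lower than the completer therefore does not depend on how the SDI sentence is read. The excess above 100% does depend on the day count.

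| Day-1 drug | Literal | Planned time kept |
|---|---|---|
| FOLFOX, 3 of 12 | 137.5% | 25.0% |
| FOLFOX, 9 of 12 | 103.1% | 75.0% |
| CAPOX oxaliplatin, 4 of 8 | 116.7% | 50.0% |
| CAPOX oxaliplatin, 2 of 4 | 150.0% | 50.0% |

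**What the literal formula does capture.** All 12 cycles with 14 days' delay: 154/168 = 91.7%. A 20% reduction throughout: 80.0%. One cycle omitted mid-course: 11/12 = 91.7%. The gap concerns only time after the last dose.

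**Protocol 4.11.** With durations of 12 and 24 weeks, (6/12)/(12/24) = 100%, so it applies no penalty either.

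**Cut points, day-1 drug, 6 of 12, literal.** Below 85% needs a delay above 6/(0.85 × 12/154) − 70 = 20.6 days, or q < 0.85/1.10 = 0.773. Below 70% needs more than 40.0 days, or q < 0.636. A 20% reduction plus stopping at 6 scores 0.8 × 110 = 88.0% literally and 0.8 × 50 = 40.0% with planned time kept, on opposite sides of both cut points.

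**Arm difference (illustration).** Suppose the resistance training (RT) stop rate is below usual care (UC) by g, all stops come after 6 of 12, and delivery is otherwise perfect. Then RT − UC = −g × (stopper's RDI − 100). For g = 0.05, 0.10 and 0.15:

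- Literal, day-1 drug (110%): −0.5, −1.0, −1.5 points
- Time to cycle end (100%): 0 throughout
- Planned time kept (50%): +2.5, +5.0, +7.5 points

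**SD.** With planned time kept, stopping alone at assumed UC/RT rates of 20%/10% gives 50 × √[(0.16 + 0.09)/2] = 17.7; at 30%/15% it gives 50 × √[(0.21 + 0.1275)/2] = 20.5. Times 0.42, these are 7.4 and 8.6 points.

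**Planned-cycle count.** For a patient randomized after 2 of 12, counting all 12 in SDI gives an on-time completer (10/126)/(12/126) = 83.3%, below 85%.

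**The case against.** The strongest reply is that the SAP does not leave the denominator sentence alone. It adds a missed-cycle method and says that early stoppage is incorporated, so the defect would be an undefined adjustment and not a formula that ignores stopping. Much of this stands. The intent is clear, and the named method may keep the time after a stop. But the SAP states neither the dose nor the days of a missed cycle, nor whether cycles after permanent discontinuation count. A stated denominator still conflicts with a stated property of a primary endpoint.

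A reader might infer that a stopper at 6 of 12 always scores 1.10 times a completer, or that a patient with a single dose has a zero denominator and no score. Both depend on exclusive day counting and a day-1 drug. Inclusive counting or a two-day infusion gives about 1.08–1.09 and a defined, though implausibly high, single-dose score. Only the lack of a penalty holds under every convention examined.

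Protocol 4.11 does commit to reporting a cycles ratio, so early stoppage does not rest on RDI alone. That ratio does not make RDI what the SAP says it is. Nor is it claimed that no arm comparison of the ratio is planned anywhere, since the SAP text available is not complete.

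**Conclusion.** The point holds as a conflict within SAP 1.1: the written delivered time base gives no penalty for permanent early stoppage, the SAP says RDI includes it, and the adjustment that could reconcile them is undefined. For FOLFOX stopped at 6 of 12 the choice is between about 100–110% and 50%. It should be settled before the analysis, because early stoppage is part of the primary objective.

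If the literal rule is programmed and RT reduces stopping, that benefit is lost from the RDI difference or enters with the wrong sign. The reversals above are small beside the 7.3-point detectable difference; the larger loss is the benefit that goes unmeasured.

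A reader might go further and conclude that the trial's RDI results are wrong or have the wrong sign. The documents do not support that. They give no stop rates, the arm differences rest on assumed rates with all stops at half course, and the analysis run may have handled stopping correctly.

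**What to change.** State one rule per drug in SAP 1.1:

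- **SDI:** starting dose/m² times cycles planned after randomization, divided by days from day 1 of the first post-randomization cycle to the last planned dose.
- **DDI:** dose/m² delivered after randomization, divided by days from the same start to the later of the last planned dose date and the last actual dose date. Every planned cycle not given counts as zero dose, including cycles after permanent discontinuation or after the follow-up visit.
- **Days:** one counting convention for both.

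This needs no classification of gaps as delays or omissions. One consequence should be stated: a delay before an early stop adds no penalty unless the last actual dose falls after the planned end. Stopping after 6 with 14 days' delay ends at day 84 of 154 and stays at 50%.

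Add worked checks (FOLFOX 12, day-1 drug): stop after 6 = 50%; stop after 1 = 1/12 = 8.3%; one omitted cycle = 91.7%; all 12 with 14 days' delay = 91.7%; randomized after 2 and the other 10 on time = 100%.

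SAP 2.1 reports that 183 participants have been randomized, so fix and date the rule before arm comparisons are seen. Report the actual/planned cycles ratio of Protocol 4.11 by arm.

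The cost is rewording and minor reprogramming. Doses, cycle start dates and the planned course are already collected under Protocol 4.11; that section does not list the last capecitabine dosing date, which may need abstracting or a convention. Mean RDI will be lower than under the literal formula, and the SD of 17.3 and detectable difference of 7.3 points should be rechecked under the clarified definition.
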